4.17.4 Serious Adverse Events

All serious adverse events should be reported to the Institutional Review Board (IRB) oversight, the FDA and Pthera LLC, as required.

If Pthera LLC or its designee notifies Investigators of any serious adverse event that is considered an unanticipated adverse effect of the device, Investigators should notify their own IRB/EC as necessary.

The investigator should report serious adverse events, serious adverse effects and serious and unexpected suspected adverse effects to the ethics committee when the event occurs or becomes known within a period of no more than one (1) calendar day. Likewise, it must report to the INS OGITT within seven (7) calendar days of the occurrence of the event or as soon as it becomes aware of the event, through the Sistema de Reporte Virtual de Eventos Adversos Serios (REAS-NET).

4.17.5 Death

Deaths reportable to Pthera LLC include all deaths during study participation.

4.17.6 Withdrawal for Adverse Events

All adverse events resulting in subject withdrawal from the study should be reported immediately by telephone to Pthera LLC.

The investigator may be asked to provide detailed follow-up information. The investigator will determine the reportability of the event on a case-by-case basis and report to the appropriate regulatory authorities evaluating the study device as necessary.

4.18 Measures to Ensure Subject's Safety

The investigator will be responsible for monitoring the safety of subjects entering this study and for alerting Pthera LLC of any study-related events that appear unusual and/or unanticipated to their facility.

The investigator will be responsible for the proper medical care of subjects during the study in relation to the protocol procedures for their center.

The investigator will remain responsible for providing appropriate medical care options after a subject terminates or the study is discontinued due to adverse events.

4.19 Subject Disposition Criteria

4.19.1 Withdrawal from the Study

Each subject and the investigator reserve the right at any time to terminate a subject's participation in the clinical investigation.

Possible reasons for withdrawal or removal from the study may include:

Transcranial Near Infrared Laser Therapy in Subjects with Major Depressive Disorder: A Laser Dosing Study.

1. The subject voluntarily withdraws consent.
2. The subject was ineligible according to the inclusion and exclusion criteria of the study.
3. The subject develops an adverse event that would not allow continuation in the study.
4. The subject has an adverse event that, in the opinion of the investigator, warrants withdrawal from the study. Pthera LLC must be notified within two business days.
5. The subject and/or the investigator make the decision that the subject should withdraw from the study.
6. Subject to death of participant.
7. Positive pregnancy test during eligibility procedures.
8. The subject misses one of the 3 scheduled sessions per week and it is not possible to make it up before the end of the week. When a subject withdraws or is withdrawn from the study, the following will be performed, if possible, at the study termination (exit) visit:
 - HAM-D-17
 - QIDS-C
 - CGI
 - C-SSRS
 - ADVERSE EVENT FORM
 - Concomitant Medication Form
 - ASQ (self-assessment)
 - SAFTEE-SI (self-assessment)
 - SDQ (self-assessment)

For all subjects who prematurely withdraw from the study, the date and reason for withdrawal will be documented.

4.19.2 *Loss of Follow-up*

If a center is unable to contact a subject or if the subject fails to appear for a visit, three documented telephone calls should be made, followed by a certified letter (or its equivalent, such as an e-mail). The certified letter should detail the need for the subject to appear for a visit, the center's failed attempts to contact the subject, and that failure to contact the center will cause the subject to be withdrawn from the study.

If the certified letter is returned to the center as undeliverable or the letter is delivered but the subject does not communicate with the center and no further contact is made with the subject or the subject's caregiver, then the subject will be considered lost to follow-up with the subject and suspended from the study. All attempts to contact the subject will be documented.

A delay in the application of the laser, not exceeding 72 hours, will be tolerated for reasons of major cause. Provided that this delay allows to comply with the 3 administrations corresponding to the week of the intervention under study. If the subject does not comply with the 3 administrations of the treatment, he/she will be withdrawn from the study.

Transcranial Near Infrared Laser Therapy in Subjects with Major Depressive Disorder: A Laser Dosing Study.

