The NIR-TLT delivery is expected to last no longer than 7.15 minutes (429 seconds) in total (simultaneous application to the left and right forehead). The subject will be allowed to rest for 5 minutes after NIR-TLT delivery. The skin at the application sites will be inspected again after laser application. A log will be kept with the dates of delivery of the NIR-TLT.

Near Infrared Transcranial Laser Therapy in Subjects with Major Depressive Disorder: A study of Dosing with Laser.

treatment per study subject. The use of cell phones, tablets, computers or electronic devices will not be allowed during laser administration.

[figure not shown]
During treatment visits and prior to NIR-TLT, study personnel will collect tolerability (safety) and efficacy data:

1. Safety data: SAFTEE-SI (self-assessed), C-SSRS, adverse events and concomitant medication form.
2. Efficacy data - HAMD-17.

In addition to the evaluation described above, during visits 1, 9 and 18:

Prior to the NIR-TLT study, the staff will collect primary efficacy data from metric measurements and brain electrophysiology data:

1. Efficiency data:
 - a. Doctor-administered scales (1): HAMD-17, QIDS-C and CGI-S.
 - b. Patient-Reported Scales (1): ASQ and SDQ
2. Brain Electrophysiology Data - Study personnel will conduct a first 10-minute EEG recording session, treat the patient according to their NIR-TLT group randomization, and then conduct a second 10-minute EEG recording session as soon as possible after the end of treatment, but within 15 minutes.

3. Exploratory PET scan data: A PET scan will be performed on the participants selected to be part of the research subgroup, before the first treatment visit and within 24 hours of the end of the last intervention (visit 18).

4.9.3 Follow-up visit (Post Treatments) - Week 8

Near Infrared Transcranial Laser Therapy in Subjects with Major Depressive Disorder: A study of Dosing with Laser.

The next visit will occur two weeks after the last cerebral blood flow impact visit.

Purpose: The purpose of the follow-up visit is to evaluate the long-term antidepressant effect of NIR-TLT.

Procedures: During the follow-up study, staff will collect tolerability (safety) and efficacy data:

1. Safety data: SAFTEE-SI (self-assessed), adverse events and concomitant medication form.

2. Efficiency data:

- a. Doctor-administered scales (1): HAMD-17, QIDS-C and CGI.
- b. Patient-reported scales (1): SDQ and ASQ.

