4.9.4 Completion

If, during the study, a subject's CGI-S increases more than 2 points or rises above a score of 5, or if they become actively suicidal according to the C-SSRS scale, the subject will be referred to their treating doctor and advised to start or switch to another FDA-approved antidepressant medication. Such subjects may or may not be terminated from the study, depending on the severity of symptoms, at the clinical judgment of the principal investigator. Subjects who are considered actively suicidal and in imminent danger will be terminated from the study and referred to the appropriate local MGH or NKI emergency room for evaluation and subsequent hospitalization, or, if the subject is appropriate for outpatient monitoring, will be referred to their treating doctor for frequent appointments and follow-up. Each subject will have the investigator's contact information, as well as instructions on how to call emergency services, if necessary. We will encourage subjects to continue enrollment in the study through follow-up visits, regardless of discontinuation of NIR-TLT.

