5.5 Efficacy and Safety Analysis for the Aims

It will be carried out as follows:

A. Antidepressant effect of NIR-TLT doses:

To compare the antidepressant effects of NIR-TLT doses, mean changes in HAM-D 17 scores (for evaluation of the Primary Assessment Criteria) and QIDS-C and CGI-S (for evaluation of the Secondary Assessment Criteria), will be performed for each dose at 3 time points (visit 1, visit 9 and visit 18) will be compared using a repeated measures ANCOVA. A significant ANCOVA interaction in mean score changes between groups will be taken as indicating that the groups have different antidepressant efficacy. If significant ANCOVA interactions are found, paired samples t-tests will be used to explore differences between scores/groups.

Both the full analysis and the analysis by intention will be performed to analyze the severity of depression at the endpoint. Patient attrition and dropout will be analyzed. The possible

Transcranial Near Infrared Laser Therapy in Subjects with Major Depressive Disorder: A Laser Dosing Study.

differences between treatment groups in dropouts will be examined with Fisher's exact test.

B. Brain electrophysiological effect of NIR-TLT doses:

To compare the effects of NIR-TLT doses on brain electrophysiology, changes in EEG spectral power in all spectral bands for each dose at 3 time points (visit 1, visit 9, and visit 18) will be compared using a repeated measures ANCOVA. A significant ANCOVA interaction in mean score changes between groups will be taken as indicating that the groups have different effects. If significant ANCOVA interactions are found, paired samples t-tests will be used to explore differences between groups.

C. Safety and tolerability of NIR-TLT doses:

To compare the safety and tolerability of NIR-TLT doses, mean changes iSAFTEE-SI scores at 3 time points (visit 1, visit 9, and visit 18) will be compared using a repeated measures ANOVA. A significant ANOVA interaction in mean score changes between groups will be taken as indicating that the NIR-TLT doses have different tolerability. If significant ANOVA interactions are found, paired samples t-tests will be used to explore differences between groups.

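### One session that cannot be made up removes the participant from the study, so the later scheduled HAM-D-17 scores needed for the intention-to-treat comparison are not collected

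*Protocol*

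**What the plan says.** Section 4.19.1 opens its list with permissive wording, "Possible reasons for withdrawal or removal from the study may include", and item 8 of that list is "The subject misses one of the 3 scheduled sessions per week and it is not possible to make it up", with the close of that same week as the deadline. Section 4.19.2 repeats the rule as an obligation: "If the subject does not comply with the 3 administrations of the treatment, he/she will be withdrawn from the study". The only relief is a short make-up window, "A delay in the application of the laser, not exceeding 72 hours, will be tolerated for reasons of major cause", and it applies only if the week's three sessions are still completed.

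For a participant who leaves, section 4.19.1 says that "the following will be performed, if possible, at the study termination (exit) visit", and the list includes HAM-D-17. No later scheduled assessment is provided for.

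Section 4.9.4 points the other way: "We will encourage subjects to continue enrollment in the study through follow-up visits, regardless of discontinuation of NIR-TLT".

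The primary criterion (section 1) is HAM-D-17 at visits 1, 9 and 18, compared by repeated measures ANCOVA (section 5.5). Section 5.5 adds: "Both the full analysis and the analysis by intention will be performed to analyze the severity of depression at the endpoint".

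The protocol is also inconsistent about when HAM-D-17 is taken. Section 4.9.2 states "During treatment visits and prior to NIR-TLT, study personnel will collect tolerability (safety) and efficacy data" and names HAM-D-17 as the efficacy item. The Table of Assessments (section 8) marks it only at screening, V1, V9, V18 and V19.

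**The concern.** The rule ends participation in the study, not only treatment, because of non-adherence. An intention-to-treat analysis is meant to keep the outcomes of non-adherent participants in their assigned arm. Here those outcomes stop being collected, so the comparison at visit 18 moves toward people who attended every session.

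If missed sessions are related to mood, perceived benefit or local side effects, the loss is informative and may differ between arms. The protocol has no data on this, so it is a risk and not a demonstrated bias. There is a route to it within the document: section 4.20.1 lists erythema, pain and discomfort at the application site as reported with this treatment, and sections 4.17.2 and 6.4 stop treatment for erythema or lasting discomfort. Anyone stopped for those reasons then fails the three-per-week requirement.

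The Fisher's exact test on dropout in section 5.5 can show an imbalance between arms but supplies no scores. A statistical analysis plan can choose a missing-data method but cannot restore assessments that the protocol ends.

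**Working it through.** **1. Can the passages be followed together?**

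| Place | Effect on someone who misses a session for good |
|---|---|
| 4.19.1 item 8 | may be withdrawn from the study |
| 4.19.2 | must be withdrawn from the study |
| 4.9.4 | encouraged to stay through follow-up after stopping treatment |

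Anyone who stops sessions before week 6 ends necessarily has an incomplete week. Section 4.19.2 then removes that person from the study, while section 4.9.4 asks that the person stay. Sections 4.19.1 and 4.19.2 also disagree on whether withdrawal is optional.

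**2. The plan's own sample size.** Inputs from section 5.3: difference 6.4, SD 7.091, alpha 0.05, power 90%, loss 20%, four arms. A one-sided two-sample t-test needs 21.74, so 22 per arm; 22/0.8 = 27.5, so 28; 28 × 4 = 112. Power at 22 per arm is 90.3%. Section 5.3 does not state sidedness. A two-sided t-test needs 27 per arm, so 34 after loss and 136 in total. The one-sided basis is therefore the one that reproduces 112. Two-sided power at 22 per arm is 83.3%.

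**3. How many would the rule withdraw?** The protocol gives no rate of unrecoverable misses. Assume a constant, independent weekly chance p over 6 weeks. The proportion withdrawn is 1 − (1 − p)^6.

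| p per week (assumed) | Withdrawn | Of 112 |
|---|---|---|
| 3% | 1 − 0.97^6 = 16.7% | 18.7 |
| 5% | 1 − 0.95^6 = 26.5% | 29.7 |
| 10% | 1 − 0.90^6 = 46.9% | 52.5 |

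The rate at which this rule alone uses the whole 20% allowance is 1 − 0.8^(1/6) = 3.65% per week, or 1 − 0.8^(1/18) = 1.23% per session.

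**4. Which scores are lost?** At 5% per week, 112 × (1 − 0.95^3) = 16.0 leave in weeks 1 to 3. A further 29.7 − 16.0 = 13.7 (46% of leavers) go in weeks 4 to 6 and already have visit 9. In weeks 1 to 5, 112 × (1 − 0.95^5) = 25.3 leave, before the week of visit 18.

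**5. Power if those withdrawn contribute nothing (worst case).** Remaining per arm is 28 × (1 − p)^6; same t-test, difference and SD.

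| p per week | n per arm | One-sided (planned 90.3%) | Two-sided (reference at 22: 83.3%) |
|---|---|---|---|
| 3% | 23.3 | 91.8% | 85.4% |
| 5% | 20.6 | 88.5% | 80.6% |
| 10% | 14.9 | 77.5% | 66.1% |

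If a further 10% is lost for other reasons (assumed), total loss is 1 − 0.9 × 0.97^6 = 25.0% at 3% (21.0 per arm, one-sided power about 89%) and 1 − 0.9 × 0.95^6 = 33.8% at 5% (18.5 per arm, 85.3%).

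**6. The assessment schedule.** If the Table of Assessments governs, the first scheduled post-baseline HAM-D-17 is at visit 9 in week 3. Section 4.7 counts a participant as analysable after three sessions in one week. A participant withdrawn in week 2 would meet that definition with no scheduled post-baseline score, and would have one only if the exit visit takes place.

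**The case against.** The strongest reply has four parts.

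- **The sentence in 4.9.4 closes a paragraph on clinical worsening and suicidality, and it only encourages.** That is true, and it never mentions missed sessions. But its wording covers any discontinuation of treatment, and even a participant who stops for worsening would have an incomplete week and fall under the mandatory sentence in 4.19.2. The conflict stands.
- **An exit HAM-D-17 is planned and can feed an endpoint analysis.** This softens the loss. The score is conditional, however, and falls at an unscheduled time, so it does not replace visit 9 or visit 18 in a comparison built on those visits. If HAM-D-17 is in fact taken at every treatment visit, as 4.9.2 reads, there would also be repeated scores up to withdrawal, but none after it.
- **The rates are assumed, and power hardly moves at the lower ones.** This is right. At 3% per week the one-sided figure stays above the planned value, and nothing says the 20% allowance excludes this cause. Counting only the 25.3 who leave before week 6 at 5% per week gives 28 × 0.95^5 = 21.7 per arm and 89.9%, essentially as planned. The two-sided shortfall from 90% comes mostly from sidedness, a separate matter. Power is therefore not the main argument.
- **Someone who cannot attend a make-up session may also miss assessments.** The fraction of scores that would be recovered is unknown.

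What remains is that the protocol chooses not to collect scheduled primary outcomes from non-adherent participants.

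**Conclusion.** The concern holds and should be fixed. From the text alone, sections 4.9.4, 4.19.1 and 4.19.2 cannot all be followed, and the mandatory version ends collection of the scheduled HAM-D-17 scores on which the primary comparison depends. The intention-to-treat analysis is weakened, not made impossible.

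The size depends on a missed-session rate that the protocol does not give. Across assumed weekly rates of 3% to 10%, with misses independent, 17% to 47% of participants would be withdrawn. The worst-case one-sided power runs from 91.8% down to 77.5%, against 90.3% planned; exit scores would reduce that loss. The power effect is modest unless misses are common. Selective loss of the outcome matters more, and its direction and size cannot be known in advance. The mismatch over when HAM-D-17 is taken is a separate inconsistency that determines how many scores an early leaver has.

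**What to change.** In sections 4.19.1 (item 8) and 4.19.2, separate stopping sessions from leaving the study. Suggested wording: *The missed session is recorded as a protocol deviation. Unless consent is withdrawn, the participant completes HAM-D-17 and the other scales at the scheduled times of visits 9, 18 and week 8.*

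State that the main analysis includes all randomised participants by assigned arm, with the fully adherent set as supportive. Whether sessions continue after a miss is for the sponsor to state when reconciling 4.9.4, 4.19.1 and 4.19.2; this review takes no position on it.

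Reconcile section 4.9.2 with the Table of Assessments on when HAM-D-17 is taken, then align the definition of analysable data in section 4.7 with the result.

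The cost is amendment wording plus at most three already scheduled assessments for each participant who would otherwise have been withdrawn. The downside is that the estimate will include people with incomplete exposure, so the effect may come out smaller than among full adherers.

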4.20 Summary of Risks and Benefits

4.20.1 Potential Adverse Events

Risks to the subject may include, but are not limited to, the following:

The EXPi device emits light with a wavelength longer than the human eye can see. Personnel will be trained in basic safety procedures related to the use of the device. Personnel administering the NIR-TLT will be careful not to operate the EXPi device unless it is in direct contact with the subject's skin. Both the subject receiving the NIR-TLT and the study doctor present in the NIR-TLT room will wear eye protection in the form of goggles or pads. The goggles provided with the EXPi device are in direct contact with the area surrounding the subject's eye. Since they are reusable, they should not be shared between subjects. The eye pads are disposable and should be discarded after use. The eye pads have an adhesive to adhere to the subject's eyelids, so there is a possibility of an allergic reaction.

EXPi device failure resulting in cessation of investigational therapy may cause:

1. No adverse events to our knowledge
2. Unforeseeable adverse events

Delivery of infrared energy to an inappropriate site, such as directly over the open eye, is not recommended and could pose a risk to the subject.

The application of the EXPi device may cause a slight thermal sensation of heat during use. The skin temperature is well below the thermal damage level.

Based on human clinical trial experience to date, each adverse event listed below has been reported with TLT:

1. Erythema at the application site
2. Pain at the application site
3. Discomfort at the application site
4. Heat at the application site
5. Reaction at the application site
6. Headache

Additional potential side effects of NIR-TLT, documented in previous trials, include:

- See bright colors, abnormal taste
- Feeling "out-of-body" experiences
- Insomnia, restless sleep, erratic sleep, early morning awakening.
- Vivid dreams
- Irritability
- Difficulty finding words
- Abdominal distention

Other potential risks are described below:

Transcranial Near Infrared Laser Therapy in Subjects with Major Depressive Disorder: A Laser Dosing Study.

Risk of worsening depression, suicidality and manic change: Worsening depression and increased suicidality are possible complications of antidepressant treatments prescribed to subjects with MDD. We will minimize this risk by selecting only subjects who do not exhibit active suicidal ideation at screening. We will also discontinue any subject who develops active suicidal ideation during the course of the study (C-SSRS) and is considered to be in imminent danger; we will then coordinate appropriate levels of care and standard antidepressant treatment (see 4.9 Termination). Manic changes are potential adverse events and will also be closely monitored during antidepressant treatment. Our strict schedule of clinical study visits will allow early recognition of treatment-emergent suicidal ideation or prodromal hypomanic signs. Subjects who develop mania or hypomania will be discontinued and provided with the appropriate level of care.

Answering detailed questionnaires may create a slight degree of inconvenience for subjects.

Duration of testing for cognitive circuitry: The total testing duration takes a total of 40 minutes at baseline and 40 minutes at weeks 5 and 9. There is no expected risk to patients beyond the 40 minutes of sitting at the computer for testing and possible startle experience. Every effort will be made to ensure that patients are comfortable and safe during this period, and the study can be stopped at any time. Beyond these problems, there is little or no risk to patients.

Risk of bruising: venous puncture may cause accidental bruising when blood is drawn from the forearms.

4.20.2 Benefits:

Study subjects will receive a systematic MINI assessment of their DSM comorbidity. This information will be readily available to their treating doctors if subjects so desire and agree to disclose. This information can guide long-term treatment. In the short term, the subject will receive close and systematic depression follow-up and formalized cognitive assessments beyond current standards of care. Easy access to routine physical examinations is also a potential benefit. Subjects will have access to a different treatment modality if counseling and/or medications were not sufficient or not acceptable to them. The treatment itself with transcranial laser therapy (TLT) can potentially alleviate depressive symptoms on a level equal to antidepressant medication.

4.20.3 Allowed and prohibited concomitant interventions:

No concomitant prohibited interventions have been reported during treatment with this device. Contraindications for use:

- Do not apply infrared light to abdominal or lumbosacral points in pregnant women.
- Do not apply infrared light to epiphyseal lines in children.
- Do not apply infrared light in the thoracic region or on the pacemaker itself in patients with pacemakers.
- Do not apply infrared light to the thyroid gland, ovaries or testicles.

Transcranial Near Infrared Laser Therapy in Subjects with Major Depressive Disorder: A Laser Dosing Study.

- Do not apply infrared light to patients who are taking
- drugs that have contraindications that are sensitive to heat or heat sensitive.
- light, such as, among others, certain types of steroids.

5. Data Analysis Methods

